SBI-HV Impacts on Client Outcomes. The study will use a randomized intent-to-treat design, with home visitors randomly assigned to condition (routine HV vs. HV+SBI-HV). Data will have a 3-level nested structure: clients (N=40) within home visitors (N=10-20) within sites. Given the small number of home visitors and sites, modeling each as a random effect would not yield stable estimates. Therefore, we will use the sandwich variance estimator to adjust standard errors as appropriate to account for nesting of clients within home visitors. Site will be included as a fixed covariate in all models. We will conduct ANOVA or chi-square tests to assess group equivalence on home visitor characteristics (demographics, EBP readiness), and client characteristics; those that differ between groups will be included as covariates. We will conduct latent growth curve (LGC) modeling in Mplus to examine the impact of study condition on change over time in primary and secondary outcomes. Mplus provides full information maximum likelihood estimation that produces unbiased parameter estimates under the assumption that the data are missing at random (MAR), and outperforms other missing data approaches even when MAR is not met. Analyses will use a 2 (study condition) X 3 (time) repeated measures intent-to-treat design. First, we will use likelihood ratio difference tests of nested models to determine the overall shape of the individual change trajectories: no change or linear change. Next, we will test unconditional models for all outcomes to obtain the average change effect. Third, we will add study condition to test its impact on initial status and change over time. Model

fit will be evaluated via chi-square, RMSEA, CFI, and TLI, and condition effects will be demonstrated by a statistically significant slope parameter, as tested by the pseudo z test, associated with study condition. For normally distributed outcomes, we will use conventional LGC models, with the appropriate estimator selected based on the distributional properties of the DVs. If client outcomes deviate substantially from normality, we will apply a negative binomial estimator, as recommended for count outcomes (i.e., days of SU) with a distribution that is skewed toward zero. Effect size estimates using Cohen's d will be calculated for all condition effects on client outcomes based on published LGC model recommendations.

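### Condition effects are judged by a z test on a sandwich variance clustered on only 10 to 20 home visitors, with no small-sample correction, so a nominal 5% test rejects too often

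*Combined protocol and SAP*

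**What the plan says.** All of this is in the combined protocol and SAP, section DATA ANALYSIS, under SBI-HV Impacts on Client Outcomes, unless another place is named.

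- The data structure is "clients (N=40) within home visitors (N=10-20) within sites". STUDY PURPOSE AND AIMS and STUDY PARTICIPANTS plan 20 home visitors and 40 clients, with home visitors as the unit of randomization.
- Random effects are set aside: "Given the small number of home visitors and sites, modeling each as a random effect would not yield stable estimates". In their place, "we will use the sandwich variance estimator to adjust standard errors as appropriate to account for nesting of clients within home visitors".
- The decision rule is that "condition effects will be demonstrated by a statistically significant slope parameter, as tested by the pseudo z test, associated with study condition".
- "Site will be included as a fixed covariate in all models". Home-visitor and client characteristics are compared between arms, and "those that differ between groups will be included as covariates".
- If the growth models do not converge, the closing part of DATA ANALYSIS switches to baseline-adjusted ANOVAs at 3 and 6 months. It does not mention home-visitor clustering again.

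No small-sample variance correction, t reference, degrees-of-freedom rule or permutation test is named. No alpha and no number of sites is given.

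**The concern.** The reason given for avoiding random effects applies equally to what replaces them. A cluster sandwich variance with a normal reference is justified by a large number of clusters. With few clusters two things go wrong in the same direction: the uncorrected variance is biased downward, and the normal distribution has tails that are too short for a variance estimated from so few units. The site term and any home-visitor covariates use up further cluster-level degrees of freedom, which a z test ignores.

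The plan treats a significant slope parameter as the evidence that a condition effect exists. Chance differences between arms would then pass that criterion more often than the nominal rate, for each continuous outcome to which it is applied.

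**Working it through.** The plan states no alpha, power or sample-size calculation, so there is no figure of its own to reproduce.

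**Inputs from the documents.** 40 clients; J = 20 home visitors (aims) or J = 10 to 20 (DATA ANALYSIS); randomization by home visitor; home-visitor sandwich; z test; site in all models.

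**Assumptions.** Two-sided alpha 0.05; g = J/2 home visitors per arm; equal caseloads (40/20 = 2 or 40/10 = 4 clients each); continuous outcome; complete data; no true effect; no step choosing between flat and linear trajectories.

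**Step 1: exact size without site.** With equal residual variances over time, the slope effect is the arm difference in (month 6 − baseline)/6, which is a difference of home-visitor means. Let SS be the within-arm sum of squares of those means.

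- Unbiased variance: (2/g) × SS/(2g − 2)
- Uncorrected sandwich variance: SS/g²
- Ratio of sandwich to unbiased: (g − 1)/g, which is 0.90 for g = 10 and 0.80 for g = 5

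Hence z = t(2g − 2) × √(g/(g − 1)), and size = P(|t(2g − 2)| > 1.96 × √((g − 1)/g)).

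- 20 home visitors: P(|t18| > 1.96 × √0.90 = 1.859) = 7.94%
- 10 home visitors: P(|t8| > 1.96 × √0.80 = 1.753) = 11.77%

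The intraclass correlation (ICC) does not enter. The documents do not say whether the software multiplies the variance by J/(J − 1). If it does, the cutoffs become 1.96 × √(18/19) and 1.96 × √(8/9), and the sizes 7.25% and 10.18%. Removing the variance bias completely but keeping z still gives 6.6% and 8.6%, so the reference distribution must change too.

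**Step 2: growth model with residual variances estimated.** If the residual variances are 1, 1, 2, the weights on the three visits move from −1, 0, 1 to −1.14, 0.29, 0.86, and the exact result no longer applies. The model was therefore simulated with freely estimated residual variances (true values 1,1,1 or 1,1,2; ICC 0 or 0.1; 10,000 trials per cell; Monte Carlo SE about 0.3 points).

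**Step 3: site as a fixed effect.** Client slopes were regressed on condition and site. Home visitors were spread evenly over 3, 4 or 5 assumed sites, with ICC 0, 0.1 or 0.2 and allocation either unrestricted or balanced within site (6,000 trials per cell before exclusions; Monte Carlo SE about 0.3–0.7 points).

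| Case | 20 home visitors | 10 home visitors |
|---|---|---|
| No site, exact | 7.9% | 11.8% |
| No site, exact, with J/(J − 1) | 7.3% | 10.2% |
| No site, free residual variances | 8.5–9.0% | 12.5–13.1% |
| Same, with J/(J − 1) | 7.8–8.2% | 10.8–11.3% |
| Site term, 3–5 sites | 9.5–14.7% | 18.4–36.7% |
| Same, with J/(J − 1) | 8.6–13.9% | 16.5–34.8% |

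With 10 home visitors and unrestricted allocation, the site rows leave out the 6–25% of layouts with fewer than two sites containing both arms. With every estimable layout kept, the upper end without the factor is 51.8%, but that figure is driven by degenerate layouts. With 20 home visitors, at most 0.1% of layouts were left out.

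**Step 4: the remedies in the same site cells.** A bias-corrected (CR2) sandwich with Satterthwaite degrees of freedom gave 3.5–5.6%. Site-adjusted home-visitor means with t on residual cluster degrees of freedom gave 4.2–5.9%.

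**The case against.** The strongest reply is about consequence. This is a pilot looking for preliminary impacts alongside feasibility, Cohen's d is planned for every condition effect, and the opening note says the longitudinal analyses were not carried out. That stands as a limit on what is at stake. It does not repair the rule, which makes statistical significance the test of a condition effect.

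Several points on size are fair:

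- At the 20 home visitors planned in the aims, the excess without site is about 3 points (7.9 − 5.0). The 11.8% belongs to the lower end of the range in DATA ANALYSIS.
- The figures with site depend strongly on an assumed number of sites. Two sites give about 9% with 20 home visitors and 15–17% with 10. With 10 home visitors in 5 sites, balancing allocation within site gives about 29%.
- The substance use outcomes in Client Measures are an abstinence rate and days of use. Neither was evaluated, so the numbers speak to continuous scales such as depression and parenting stress.
- The remedies were tested on client slopes with complete data and equal caseloads, and not within the full growth model.

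The fallback ANOVAs do not answer the point, because non-convergence triggers them and test size does not. On a natural reading the instruction to include site in all models does cover them. What remains open there is whether they keep the adjustment for home-visitor clustering.

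**Conclusion.** The concern holds. For a continuous outcome with complete data, the rule as written exceeds a nominal 5% in every case examined. The exact no-site figures are the firm ones, because they need neither an ICC nor a number of sites. The larger figures with site show the direction, and their size depends on the assumed sites and layout.

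No size is claimed for the whole decision procedure. Besides the binary and count outcomes, three features were left out: missing data, covariates chosen for observed imbalance, and the preliminary test meant to "determine the overall shape of the individual change trajectories: no change or linear change". The point should be corrected in the written plan. No result from these models is affected, because none was produced.

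**What to change.** Replace the z reference with small-sample cluster inference that counts the degrees of freedom used by site and home-visitor covariates. Two workable forms are:

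- (a) a CR2 home-visitor sandwich with Satterthwaite degrees of freedom;
- (b) home-visitor means of client change, adjusted for site, with t on the residual cluster degrees of freedom.

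Either can be the test itself or a check reported beside the growth model. Say that the fallback ANOVAs use the same cluster-level inference and the site term. State alpha and the expected number of sites.

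The cost is SAP wording and some analysis outside Mplus, with no extra clients. There are two downsides.

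1. **Power.** The critical value rises from 1.96 to the values below. The last column is the power for an effect that a valid z test would detect with 80% power (noncentrality 1.96 + 0.84 = 2.80, noncentral t).

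| Layout | df | Critical value | Power |
|---|---|---|---|
| 20 home visitors, no site | 20 − 2 = 18 | 2.10 | about 75% |
| 10 home visitors, no site | 10 − 2 = 8 | 2.31 | about 69% |
| 10 home visitors, 5 sites | 10 − 5 − 1 = 4 | 2.78 | about 56% |

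2. **Missing data.** Option (b) gives up the full-information likelihood handling on which the plan relies. That is a reason to use (b) as a check beside the growth model.

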The primary study aim is to conduct a pilot randomized controlled trial (RCT) to (1) assess feasibility, acceptability, and fidelity of SBI-HV, and (2) determine the preliminary impacts of SBI-HV on client symptom reduction (SU, depression, parenting stress), retention in HV, engagement in SU treatment, and alliance between the home visitor and client. The pilot RCT will be conducted in New Jersey, in counties that are implementing the Healthy Families America (HFA) home visiting program. We will enroll 20 home visitors and 40 clients. The pilot RCT will be a cluster-randomized trial, with home visitors randomly assigned to study condition. Feasibility, acceptability, and fidelity will be assessed via home visitor and client interviews and fidelity checklists. Clients will be assessed at baseline, and 3- and 6-month follow-up to track SBI-HV impacts on outcomes.

STUDY PARTICIPANTS

The study will be conducted within New Jersey (NJ)'s HV system within the Healthy Families America (HFA) HV program. Participation will be offered to all HFA home visitors throughout the state

Home Visitors

We will enroll 20 HFA home visitors in the trial. Based on our prior research with this population, we expect the home visitors to have the following demographic characteristics: 100% female, average age 36 years, 25% White, 40% Latina, 30% Black, average 5 years HV experience, and 60% with greater than a high school education.

Clients

We will enroll 40 clients who meet the following study eligibility criteria: (1) speak English or Spanish; (2) age 18 years old or older; (3) pregnant or up to 3 months postpartum; (4) enrolled in HFA with a participating home visitor within the prior six months; (5) reporting binge drinking or illicit drug use in the 3 months prior to their most recent pregnancy and not currently attending substance use treatment; and (6) have access to smartphone or other internet-enabled device with internet connection. Based on prior work with this population, we expect clients to have the following demographic characteristics: 40% Latina, 41% White, 34% Black,

63% single, 22% with a high school education or less, 78% unemployed, 85% on public assistance, and 15% child welfare system-involved.

STUDY CONDITIONS AND HV-SBI COMPONENTS FOR EACH CONDITION

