RECRUITMENT, ENROLLMENT AND RANDOMIZATION PROCEDURES

Home Visitors

The PI will schedule a group zoom meeting for all HFA home visitors in New Jersey's HFA network to introduce the study. Following that meeting, home visitors who are interested in possibly participating will be invited to schedule a one-on-one zoom meeting with the PI. During the one-on-one meeting, the PI will explain the study in detail and review the informed consent form. A pdf version of the informed consent form will be sent to the home visitor via email prior to the zoom meeting so that they can follow along as the PI reviews it. Home visitors will be given the opportunity to ask questions about the study and the consent form. Once all questions are answered, the PI will ask the home visitor if they would like to make a decision right then whether to enroll or if they would like to take some time to think about it. If the home visitor would like time to think about it, the PI will call the home visitor back at a later time specified by the home visitor. When a home visitor decides to enroll, he/she will sign the pdf version of the consent form via DocuSign and then email it back to the PI. The PI will sign via DocuSign as well and then email a fully signed copy back to the home visitor for their records. Signing the consent form constitutes enrollment into the study. Following enrollment, the PI will use a computerized randomization program to randomly assign home visitors to study condition (Intervention or Control).

Clients

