Clients will be assigned to home visitors according to usual site procedures. Home visitors will introduce the study to all clients who meet eligibility criteria (English or Spanish speaking; 18 or older; pregnant or within 3 months postpartum; enrolled in HFA within the prior 6 months) at the enrollment visit (for newly enrolling clients) or at the next available visit (for clients already enrolled within the prior six months) using a script provided by study staff. Home visitors will ask clients for their permission to provide their contact information to the study team. If permission is granted, the home visitor will provide the client's contact information to a study RA, who will contact the client by phone and conduct a brief eligibility screen (data will be retained anonymously). Home visitors will also give clients the option to contact the study team themselves, if they prefer, rather than having home visitors provide their contact information to the study team. If the client is eligible, the study RA will explain the study in more detail and ask the client if she is interested in enrolling. If the client says yes, the RA will send the client a link to a pdf copy of the informed consent form via email or text (depending on client preference). After giving the client a few minutes to review the consent form, the RA will review the main points in the consent form and ask the client if she has any questions. After answering all questions, the RA will ask the client if she would like to decide now whether or not to enroll, or would like to take more time and receive a call back later from the RA. If the client would like more time, the RA will call the client back at a time specified by the client. Once the client decides to enroll, the RA will ask her to sign the pdf of the consent form using DocuSign and send it back to the RA. The RA will then sign as a witness, and send the pdf to the PI for her signature, also using DocuSign. After obtaining all signatures, the RA will send a final signed pdf of the consent form back to the client for her records. After the informed consent process is complete, the RA will either send the client a link to complete the baseline assessment online (via a Qualtrics survey), or schedule an appointment to complete the baseline assessment with the client via phone or video-conference, depending on the client's preference. Signing informed consent and completing the baseline assessment constitutes enrollment into the study. Clients are assigned to whichever study condition their home visitor is assigned to.

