Timeframe	Activity	Person Responsible
Home Visitor Recruitment, Enrollment, and Training [October 2020-December 2020]		
At Quarterly Supervisors' Meeting in October	HELP staff introduce study to HFA supervisors at Quarterly Supervisors' Meeting (via Zoom)	PI, RAs
Scheduled for Oct-Nov 2020	HELP staff introduce study to home visitors in NJ HFA network (via Zoom)	PI, RAs
	Home visitors sign informed consent and enroll in study via individual Zoom meetings with PI	PI, RAs
	Home visitors are randomized to condition	PI
After home visitors enroll [Dec 2020]	Home visitor training [pre-recorded videos plus live zoom sessions]-intervention and control groups trained separately	PI, RAs, Home visitors
Client Recruitment and Enrollment [January 2021-October 2021]		
At HFA enrollment visit OR next visit after client is identified as eligible	Home visitors introduce study (using script) to all clients meeting eligibility criteria: newly enrolling or enrolled within the last 6 months; speak English or Spanish; 18 years or older; pregnant or within 3 months postpartum.	Home visitors
Weekly	Home visitors provide client contact information to HELP staff	Home visitors
Ongoing	HELP RAs contact client, conduct eligibility screen, and obtain informed consent from eligible clients who are interested in participating.	RAs
Within 1 week of consent	Client completes baseline assessment [either via Qualtrics link or via phone with RA, depending on client preference]	RAs, Clients
Upon completion of baseline	RA informs home visitor that client has enrolled and completed baseline interview and to do Introduction at next home visit (content differs by condition)	RAs
Implementation of HV-SBI Components [January 2021-December 2021]		
At next home visit	Home visitor completes Introduction: Alcohol & Other Drugs (for intervention group) OR Introduction: Nutrition (for control group)	Home visitor
After home visit	RA sends home visitor text-based fidelity checklist to determine whether Introduction was completed	RAs

	Home visitor completes text-based fidelity checklist	Home visitor
Within 2 weeks of baseline	RA prompts client to complete HELP Session 1 (content differs by condition) within 2 weeks of baseline date and provides technical support by phone or text as needed	RAs
Within 2 weeks of baseline	Client completes HELP Session 1	Clients

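### Site is adjusted for in every model, but no stratification of home-visitor randomisation by site is described, so chance imbalance within sites costs precision

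*Combined protocol and SAP*

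**What the plan says.** Under Data Analysis (SBI-HV Impacts on Client Outcomes), the plan describes the hierarchy: "Data will have a 3-level nested structure: clients (N=40) within home visitors (N=10-20) within sites". It rejects random effects for the upper levels: "Given the small number of home visitors and sites, modeling each as a random effect would not yield stable estimates". Sandwich standard errors are to handle clients within home visitors, and for the level above it says "Site will be included as a fixed covariate in all models".

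Allocation is described under Recruitment, Enrollment and Randomization Procedures (Home Visitors): "Following enrollment, the PI will use a computerized randomization program to randomly assign home visitors to study condition (Intervention or Control". For clients, the same section says "Clients are assigned to whichever study condition their home visitor is assigned to". Neither these passages nor the aims, the study conditions section or the timeline mentions stratification, blocking, minimisation or any other use of site in the allocation. They do not rule it out either.

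The number of sites, and of home visitors per site, is not stated. Nothing says what happens if a site has home visitors in one arm only.

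**The concern.** Condition varies only between home visitors. Once each site has its own term, a comparison between sites tells the model nothing about condition; only home visitors in different arms at the same site do. If the allocation takes no account of site, some sites will by chance be lopsided and some may sit entirely in one arm. Clients at a one-arm site then help to estimate that site's level but not the arm effect.

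With at most 20 randomised units, what is at stake is the width of the interval around the preliminary effect estimates that the pilot is meant to supply. The loss is avoidable, because the home visitors are all recruited before any client is.

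**Working it through.** The plan gives no power or precision figure, so there is none to reproduce.

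**Inputs**
- Home visitors and clients, from Study Purpose and Aims: "We will enroll 20 home visitors and 40 clients".
- Home visitors in the analysis: 10 to 20 (Data Analysis).
- Number of sites S: not stated, only called small. Range assumed: 2 to 10.
- Allocation ratio: not stated for home visitors. A 10:10 split is assumed; it agrees with the example of 20 women in the experimental condition under Implementation Data Collection.
- Each home visitor is given equal weight (40/20 = 2 clients each), an assumption.

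**Step 1. Information.** With site terms, information on the arm effect is proportional to the sum over sites of t(n − t)/n, where n is the number of home visitors at the site and t the number in the intervention arm. With H home visitors, perfect balance in every site gives H/4, which is 20/4 = 5. A one-arm site gives 0.

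**Step 2. Mean under an unstratified 1:1 split.** Two given home visitors are in different arms with probability H/[2(H − 1)], so the expected t(n − t) is [n(n − 1)/2] × H/[2(H − 1)]. Dividing by n, summing over sites and dividing by H/4 gives a mean retained share of (H − S)/(H − 1). This mean does not depend on how home visitors are spread over the S sites.

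**Step 3. Twenty home visitors, 10:10, equal sites.** There are 184,756 ways to choose 10 of 20. The standard-error factor is 1/√(mean share). The one-arm chances come from simulated allocations.

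| Sites | Mean retained | SE factor | Chance of at least one one-arm site | Chance that every site is one-arm |
|---|---|---|---|---|
| 2 | 18/19 = 95% | 1.03 | about 0% | 2/184,756 = 0.001% |
| 4 | 16/19 = 84% | 1.09 | 11% | 6/184,756 = 0.003% |
| 5 | 15/19 = 79% | 1.13 | 34% | impossible (10 is not a multiple of 4) |
| 10 | 10/19 = 53% | 1.38 | 99% | 252/184,756 = 0.14% |

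Unlucky allocations do worse: the 5th percentile of retained information is 84%, 50% and 20% at 2, 5 and 10 sites. With 10 sites of two, a given site is one-arm with probability 9/19 = 47%. Coin-toss allocation gives a mean of (H − S)/H: 90%, 80%, 75% and 50%.

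**Step 4. Fewer home visitors.** If only 10 are randomised, 5:5, the mean is (10 − S)/9: 89%, 67% and 56% at 2, 4 and 5 sites. If 20 are randomised and a random 10 contribute clients, the unstratified mean is about 84%, 64%, 55% and 25% at 2, 4, 5 and 10 sites, relative to those 10 in perfect balance.

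**Step 5. With stratification by site.** If all 20 contribute and sites are equal, retained information is 100% at 2, 5 and 10 sites. At 4 sites of 5 it is 4 × (2 × 3/5)/5 = 4.8/5 = 96%. With uneven sites (20 home visitors, 10 sites) it is about 79%, against 53% unstratified; sites with one home visitor still contribute nothing if each keeps its own term. If a random 10 of 20 contribute, stratified allocation keeps about 89%, 73%, 70% and 47% at 2, 4, 5 and 10 sites.

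**The case against.** Four arguments weigh against the point.

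- **Silence is not exclusion.** A computerised program may well have a site stratum. This stands: the supportable statement is that none is described, and one sentence from the sponsor could settle it.
- **The model is valid.** A reader might infer that allocation and analysis conflict, so that the adjusted estimate is biased. The documents do not support that. Adjusting for a factor not used in the allocation introduces no bias, and the site term removes chance differences between sites. The figures above count the cost of the site term but not any residual variance it removes. Stratifying keeps that benefit while avoiding most of the cost.
- **The arm effect remains estimable.** A reader might infer that the site-adjusted model is close to non-estimable. With 20 contributing home visitors this is not so: the effect is lost only if every site is one-arm, at most 0.14% in the scenarios shown. It becomes material only in an extreme case. If a random 10 of 20 home visitors contribute across 10 sites, the chance is about one in five; at 2 to 5 sites it is about 2% or less.
- **Practical weight is low.** The plan calls the number of sites small, and at 2 to 4 sites the mean loss is only 5% to 16%. The client effects are preliminary aims of a pilot. The opening note says randomisation was eliminated and the planned longitudinal analyses could not be carried out. This stands too, and limits the severity.

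**Conclusion.** The point holds as a minor one about the plan as written. Site enters every model, no site-stratified allocation is described, and the expected result is lost precision on the arm effect. The loss ranges from about 5% of the information at 2 sites to about 47% at 10, for 20 home visitors split 10:10 with equal weight, and is larger if fewer contribute clients. The mean does not depend on equal site sizes, but the one-arm chances and percentiles do. Where the trial would have fallen in this range cannot be told, because the number of sites is not given.

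**What to change.** State the number of sites. Randomise all enrolled home visitors in one batch, stratified by site, with sites that have a single home visitor pooled into one stratum. Define the site covariate by the same strata, pooled in the same way. Pooling in the allocation alone does not help: a single-visitor site with its own model term still adds nothing to the arm effect. State in advance how a site left with contributing home visitors in only one arm will be handled.

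The timeline allows this. Home visitors are recruited from October to December 2020, their training is placed at "After home visitors enroll [Dec 2020", and client recruitment starts in January 2021.

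The cost is a setting in the randomisation program and a sentence each in the randomisation and analysis sections. Early enrollers wait for the batch, and the pooled sites are not adjusted for individually. Balance is only partly kept if some home visitors contribute no clients.
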